1. BACKGROUND AND RATIONALE

In Singapore, the Ministry of Health has declared a “War on Diabetes” and major efforts will be made to develop and deploy programs to prevent diabetes. One of the cornerstones of diabetes management involves dietary modifications to reduce postprandial hyperglycaemia. However, implementation of a low GI diet is highly complex requiring the individual to choose foods from a long list which are primarily based on western consumption patterns. Many foods in the Asian diet, which largely consist of carbohydrates such as white rice, noodles and other flour based products, are not represented. An alternative solution will require innovative ways to alter commonly available food products that will not only help reduce postprandial glycaemia but also preserve the sensory characteristics of the foods to create a new generation of food products both functional and palatable.

1.1.General Introduction

Lifestyle modification, in particular adopting an appropriate dietary pattern, is generally accepted as the cornerstone for the treatment of people with type 2 diabetes. Consumption of low GI food has shown to improve glycemic control, lipid profile and reduce systemic inflammation. However, there are few dietary intervention studies attempting to change the GI of food by changing the staple carbohydrates. In this study, formulated rice with special fibre enrichment, Diabetec® Fibre Grain (Fibre Grain), was used to replace rice as the staple carbohydrates in one's diet. This fibre enriched rice has been previously tested to have a lower GI than normal rice while still able to preserve all the sensory characteristics of normal rice. With rice being a staple to many Singaporeans, this specially formulated fibre enriched rice offers a lower GI alternative to the conventional rice without affecting the people dietary preference.

1.2.Rationale and justification for the Study

a. Rationale for the Study Purpose

Research has confirmed that a food's glycemic effect cannot be accurately predicted from the type and amount of carbohydrates it contains, as the rate at which the carbohydrates is digested and released into the bloodstream is influenced by many factors such as the food's physical form, its fat, protein and fibre content, and the chemical structure of its carbohydrates. For these reasons, it is possible to produce food from the same group with different effects on blood glucose.

b. Rationale for Test food

Previously, specially formulated Diabetec® Fibre Grain (Fibre Grain) was tested to have a lower GI as compare to normal rice grains. Thus, clinical trial is proposed to test the effect of rice in a mixed meal setting where side dishes are prepared and served in combination with the rice.

c. Rationale for Study Population

We have chosen generally healthy individuals in Singapore as the trial aim to produce rice with lower GI and better glycemic response for the general population.

d. Rationale for Study Design

A within-subject cross-over trial is proposed to investigate the glycemic response of incorporating fibre enriched rice into a mixed meal containing a protein source and vegetables. This is to investigate whether the fibre enriched rice is able to lower the glycemic response in a mixed meal setting. The results of this study would be useful in determining short and intermediate effects of alterations in the type of carbohydrate over a short or intermediate period. If initial benefits are identified, this will strengthen the reasons to evaluate this intervention over a longer period of time. This specially formulated rice can also be an alternative solution to manage the problem of diabetes without the need for change in dietary preference.

2. HYPOTHESIS AND OBJECTIVES

2.1.Hypothesis

Partial replacement of white rice with Fibre Grain will have a lower glycemic response than normal white rice in a mixed meal setting.

2.2.Primary Objectives

The primary aim of the study is to investigate the effects of partial replacement of white rice with Fibre Grains in a mixed meal setting commonly consumed by Asian Singaporeans.

2.3.Potential Risks and benefits:

a. End Points - Efficacy

The anticipated benefit is contribution to knowledge of diabetes management which may help mitigating the disease in the future.

b. End Points - Safety

Minimal risk is anticipated. Some discomfort, pain, bleeding or bruising at the site of the needle stick may occur during collection of blood samples.

3. STUDY POPULATION

3.1.List the number of subjects to be enrolled.

The number of subjects to be enrolled is 25.

3.2.Criteria for Recruitment

Potential subjects will be called up and screened for eligibility by personnel according to the inclusion and exclusion criteria. The research staff will identify potential candidates and will explain the purpose, reason and study protocol. In addition, the participant information sheet will be provided for the candidates to read prior to their decision to participate in the study. The candidates will be encouraged to ask question about the study and have adequate time to make a decision. All subjects are to give informed consent before enrolling into the research. The subsequent visit and any other administrative details will be arranged between the research staff and participant.

3.3.Inclusion Criteria

- 1 Ability to give informed consent
- 2 Age between 21-65 years old
- 3 Overtly healthy males or females, as determined by medical history, physical examination and laboratory results within normal reference range for the population or investigator site, or results with acceptable deviations that are judged to be not clinically significant by the investigator
- 4 Males and females with stable medical problems that, in the investigator's opinion, will not significantly alter the performance of the biomarker panel, will not place the subject at increased risk by participating in the study, and will not interfere with interpretation of the data.
- 5 Not on any regular medications (western / traditional medicine). Nutritional supplements with established chemical composition that can be ascertained and clearly recorded is acceptable.

However, subjects using traditional medicine (with compositions that cannot be ascertained) will be excluded in this study.

- 6 Have venous access sufficient to allow for blood sampling as per the protocol
- 7 Reliable and willing to make themselves available for the duration of the study and are willing to follow study procedures
8. Family history of diabetes (Parents and/or grandparents with history of diabetes).

3.4.Exclusion Criteria

- 1 History or presence of current cardiovascular, respiratory, hepatic, renal, gastrointestinal, endocrine, hematological, malignancy or neurological disorders capable of significantly altering the performance of the biomarker panel; or of interfering with the interpretation of data
- 2 Known or ongoing psychiatric disorders within 3 years
- 3 Regularly use known drugs of abuse within 3 years
- 4 Women who are pregnant or lactating
- 5 Have donated blood of more than 500 mL within 4 weeks of study enrolment
- 6 Have an average weekly alcohol intake that exceeds 21 units per week (males) and 14 units per week (females):
 - 1 unit = 12 oz or 360 mL of beer;
 - 5 oz or 150 mL of wine;
 - 1.5 oz or 45 mL of distilled spirits
- 7 Uncontrolled hypertension (blood pressure [BP] >160/100mmHg
- 8 Active infection requiring systemic antiviral or antimicrobial therapy that will not be completed prior to Study Day 1
- 9 Treatment with any investigational drug, or biological agent within one (1) month of screening or plans to enter into an investigational drug/ biological agent study during the duration of this study
- 10 Known allergy to insulin
- 11 History of bleeding diathesis or coagulopathy
- 12 Any of the following laboratory values at screening:

Fasting glucose $\geq 126\text{mg/dL} (\geq 7\text{mmol/L})$ or 2 hour post-prandial glucose $\geq 200\text{mg/dL} (\geq 11.1\text{mmol/L})$
- 13 Clinically significant (as determined by investigator) abnormalities on laboratory examination that will increase risk to the patient or interfere with data integrity
- 14 Have any other conditions, which, in the opinion of the Investigator would make the subject unsuitable for inclusion, or could interfere with the subject participating in or completing the study
- 15 Significant change in weight (+/- 5%) during the past month

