4. TRIAL SCHEDULE

4.1. Study Visits and Procedures

(a) Visit 1 - Screening

Volunteers will be interviewed and screened by study personnel. If the volunteer satisfies the inclusion and exclusion criteria, a written informed consent will be obtained from all selected volunteers prior to their participation in the study. Volunteers will have the study explained to them by a study personnel, will read the consent form, have the opportunity to ask questions, and then sign the approved written Informed Consent form and keep a copy. The study personnel will then proceed to schedule visit 2 and 3 with the participant.

(b) Visit 2 - Installation of CGMS (Day 1)

Upon arrival, the participant will be educated on how to maintain and care for a CGMS and to keep a food and activity diary for the duration of the CGM. During this period (Day 1-14), participants will receive SMS to check on the CGMS. If there is a need, the research personnel will arrange for a mutually convenient time and place to review and replace the CGMS. Then, the participants will proceed to take the first MMTT.

Mixed meal tolerance test (MMTT)

Before the test, measurement of participants' height, BMI, waist and hip circumference, will be done and recorded. Next, participants will be asked to attend the MMTT protocol. The participant will need to fast (no food or drinks, except plain water) from 10 pm the night before or for approximately 10-12hr prior to the study visit. No food except clear water should be

consumed. A cannula will be inserted into the participant's forearm and the cannula will remain for blood sampling only. A fasting sample will be taken for the immediate measurement of glucose while other samples for insulin, gut hormones (GLP-1, GIP, Peptide YY, Ghrelin, and Glucagon), and other metabolites will be taken, processed, stored and analysed in batches at a later stage. Then, the participant will be given either mixed meal with controlled rice or mixed meal with test rice. At 0, 15, 30, 45, 60, 90, 120 minutes, blood will be sampled through a cannula from one of the arms. Subjects will be asked to remain seated throughout the visit and only minimal movement is allowed. Blood-taking will be conducted in room designated and approved for phlebotomy purposes. Only trained personnel and/or trained nurses will be conducting the blood drawn.

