At each time point, the participant will also be given a visual analogue scale (VAS) to indicate how they feel in response to given statements by marking an "X" on a 100-mm line. For example, "How strong is your desire to eat? " Response: Very weak (0 mm) to very strong (100 mm). Appetite was evaluated using a 100 mm VAS. At time 15 min, palatability of the treatment will be assessed by five characteristics, from bad (0 mm) to good (100 mm). These characteristics were visual appeal, smell, taste, texture, and overall pleasantness of the meal given. Scores were determined by measuring the distance (in mm) from the left starting point of the line to the intersection of the "X". The average scores and AUC will be calculated and compared between the two meals

(c) Continuous glucose monitoring (Day 1 - 14)

For the next 14 days, participants will be provided with lunch and dinner from the research team through delivery. They will be randomized to receive either mixed meal with controlled rice or mixed meal with Fibre Grain rice for day 1 to 7 and received the alternative for the day 8- 14. Participants will not be told whether they are receiving the Fibre Grain rice or control rice

(d) Visit 3 (Day 14 of CGM) – MMTT2 and removal of CGMS

On day 14, participants will return to undergo the second MMTT. Their height, BMI, waist and hip circumference will be measured and recorded. Participants will be asked to attend the same MMTT protocol (refer to Day 1 – MMTT protocol). Lastly, they will return the CGMS, and your 14-day food and activity diary

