6. STATISITCAL METHODS

The sample size was calculated based on Glycaemic Index Research Report #1719 conducted by Sydney University's Glycaemic Index Research Service on the 30% Fibre Grain replacement.

Based on the primary outcome of detecting a difference of 27 units in incremental area under the curve (iAUC) from 0 to 120 minutes (iAUC 0-120min) between control and 30% fibre enriched rice and a standard deviation of 25 units in iAUC 0-120min, calculations showed that with $\alpha = 0.05$, and power of 0.9, at least 21 subjects were needed. To account for possible subject attrition during the study, 25 subjects were recruited.

All data will be analyzed using statistical software (eg. SPSS/Stata), with significance defined as a p value of less than 0.05 on a 2-sided paired t-test. Other variables will be presented as mean \pm SE with differences between groups assessed by mixed model for categorical variables and continuous variables. Data will be explored for assessment of errors, missing values, and distribution of the variables. Evaluable subjects will be those who meet eligibility and have no missing values for calculating area under the curve (AUC). Variables that will be obtained include:

For CGM profile, paired t-test will be used to compare the fibre enriched rice meal and normal rice meal group in the following:

- a. Mean of interstitial glucose (IG) per 24 hours
- b. Postprandial peak IG (highest level after meal at breakfast, lunch and dinner)
- c. Postprandial time to peak IG (at breakfast, lunch and dinner)
- d. Mean amplitude of glycemic excursion (MAGE) to assess variability. This is determined by calculating arithmetic mean of the difference between qualifying consecutive peak and nadirs. Glucose excursions > 1 SD of the mean glucose concentrations will be included.

For postprandial glucose profile after the single meal:

- a. Plasma fasting and postprandial glucose (mmol/l), insulin (mU/l) and gut hormones.
- b. The incremental AUC (0-2h) will be derived from the glucose concentration profile during the meal test (defined as the area under the glucose curve that is over the basal value taken at time). Differences between the two meals will be analyzed by paired t-test

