7. TRIAL MATERIALS

7.1. Trial Product

Research collaborator, Alchemy Foodtech Pte Ltd, will be providing the fibre grains to be used in the clinical studies. Diabetec® Fibre Grains are extruded rice-shaped grains made from Alchemy's patent glycemic lowering composition. The relevant patent title is 'GLYCEMIC REDUCING COMPOSITION' with application number 'PCT/SG2017/000003' claiming priority from 'GB 1602626.2'. The patent is under the inventor: 'Alchemy Foodtech Pte Ltd' and '[name]'. Material safety data sheets are attached.

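### The only allergy exclusion names insulin, which the trial measures but never gives; no criterion specifically names allergy or intolerance to the study meals or Fibre Grain

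*Combined protocol and SAP*

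**What the plan says.** Section 3.4, criterion 10, excludes anyone with "Known allergy to insulin". It is the only criterion in sections 3.3 and 3.4 that concerns an allergy.

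Insulin appears elsewhere as an analyte. In the MMTT description in section 4.1(b), "other samples for insulin, gut hormones (GLP-1, GIP, Peptide YY, Ghrelin, and Glucagon), and other metabolites will be taken", and "the cannula will remain for blood sampling only". Section 6 lists it among the outcome variables: "Plasma fasting and postprandial glucose (mmol/l), insulin (mU/l) and gut hormones".

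The intervention is food. Section 1.2(d) describes "incorporating fibre enriched rice into a mixed meal containing a protein source and vegetables". Under section 4.1(c), "participants will be provided with lunch and dinner from the research team through delivery", with one type of rice "for day 1 to 7 and received the alternative for the day 8- 14". Section 6.1 gives Fibre Grain at one MMTT and control rice at the other. Section 5 says a caterer prepares the meals. Section 7.1 describes the test product as "extruded rice-shaped grains made from" a patented composition and refers to attached safety data sheets.

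The safety paragraph of section 2.3 expects minimal risk and describes only local effects of blood sampling.

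**The concern.** An eligibility list should screen for hazards that participants will meet. Here the one allergy rule concerns a substance nobody is given, and nothing explicit covers what they will eat. Section 3.2 has study personnel screen volunteers against the written criteria, so the list shapes what gets asked. An otherwise healthy volunteer with a food allergy could pass through it without the subject being raised.

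The first thing at stake is participant safety: most of the meals are delivered, and the protocol does not describe anyone supervising them. The second is adherence. Someone who cannot eat the protein source or vegetables, which accompany both types of rice, may leave food or withdraw. That would blur the comparison of the two continuous glucose monitoring (CGM) weeks.

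**Working it through.** No formula applies. The check is a comparison of texts and a count.

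**Step 1. Is insulin ever given?** Every mention was read. In section 4.1(b) it is assayed from samples drawn through a cannula reserved for sampling. In section 6 it is an outcome in mU/l. The only remaining mention is exclusion 10 itself. Procedures that administer insulin: 0.

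**Step 2. What is given?** Inputs are 2 delivered meals a day for 14 days in two 7-day blocks (section 4.1(c)) and two MMTTs, one with each rice (sections 4.1 and 6.1).

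| Exposure per participant | Total | With Fibre Grain |
|---|---|---|
| Delivered meals | 14 × 2 = 28 | 7 × 2 = 14 |
| MMTT meals | 2 | 1 |
| All study meals | 28 + 2 = 30 | 14 + 1 = 15 |

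These are upper limits that assume both meals are supplied on every day, including the visit days. The protein source and vegetables come with all of the meals; Fibre Grain comes with half of them.

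**Step 3. Does any criterion name this exposure?** Section 3.3 has 8 inclusion criteria and section 3.4 has 15 exclusion criteria, 8 + 15 = 23. Criteria that name food allergy, food intolerance or dietary restriction: 0 of 23. The nearest are:

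| Criterion | What it could catch | Why it does not prompt the question |
|---|---|---|
| Inclusion 3 | A known allergy that surfaces in the medical history | Asks for general health, not diet |
| Inclusion 4 | A stable medical problem that raises risk | Rests on investigator opinion; a food allergy may not be reported as a medical problem |
| Inclusion 7 | Someone unwilling to follow procedures, including eating the meals | Depends on the volunteer knowing the ingredients |
| Exclusion 1 | A gastrointestinal disorder that affects biomarkers or interpretation | Limited to listed disorders with that effect |
| Exclusion 14 | Any condition making a person unsuitable or hindering completion | Discretionary; works only once the condition is known |

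**Step 4. Does the risk section fill the gap?** No. Section 2.3 mentions no food-related risk.

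**The case against.** The strongest reply is that the existing criteria already let an investigator keep a food-allergic volunteer out. The medical history under inclusion 3 is a natural place for an allergy to come up. Inclusion 7 bears on people unwilling to eat the meals. Exclusion 14 covers both unsuitability and inability to complete the study. Volunteers also have the study explained and can ask questions before consenting. All of this stands: the list gives real but partial cover, and it would be wrong to say that nothing protects these volunteers or that exclusion 14 is the only safeguard.

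It is also fair that exclusion 10 does little harm in itself. Exclusion 12 rules out diabetic-range glucose and inclusion 5 rules out regular medication, so the criterion is unlikely to turn anyone away.

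The safety data sheets, the consent pages and one other part of the document are absent from the text available for review, and could contain allergen information or a dietary question. That limits any prediction of what a site would actually ask. It would not make such a question an eligibility criterion, nor explain exclusion 10.

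A reader might infer three stronger points that the documents do not support:

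- That Fibre Grain is eaten for 14 days. Only the catered meals run that long; Fibre Grain is assigned to 7 days and one MMTT.
- That the gap threatens the study's power. One loss is 1/25 = 4% of those enrolled, but that is true of a loss for any reason, and no allergy or refusal rate is given. Section 6 already recruits 25 against a requirement of 21, a margin of 25 − 21 = 4, and section 3.6 has a replacement rule. The primary outcome is iAUC at the MMTTs, so uneaten delivered meals mainly affect the CGM comparisons.
- That sensor adhesive should be screened for on the same grounds. The documents do not mention it.

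**Conclusion.** The point holds as a mismatch between the eligibility list and the intervention. The sole allergy criterion corresponds to 0 exposures, while up to 30 study meals per participant, 15 of them assigned to Fibre Grain, have no criterion that specifically names allergy or intolerance. Five other criteria offer discretionary cover without prompting anyone to ask.

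The conclusion rests on the visible text of sections 3.3 and 3.4 and assumes that sites screen from that list, as section 3.2 says. How many volunteers would be affected is unknown. That exclusion 10 was carried over from another protocol is a plausible inference, since section 10.1 states hypotheses about a different food product, but it is not established and the point does not need it.

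This is a cheap improvement to participant safety and meal adherence. It does not alter the sample size or the primary analysis.

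**What to change.** Replace exclusion 10 with: *Known allergy or intolerance to any ingredient of Fibre Grain or the study meals, or a dietary restriction that prevents eating them.* Apply it at screening, before randomisation, against the manufacturer's and the caterer's ingredient lists. Reconcile the risk paragraph of section 2.3 with what participants are given, so that it covers the food as well as blood sampling.

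The cost is a short amendment, one screening question and obtaining the two ingredient lists. The downside is that a few volunteers may be excluded.

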3.5. Withdrawal Criteria

1. Any serious adverse events.
2. Participants may withdraw from the study if they decide to do so, at any time and irrespective of the reason. The reasons given will be documented.
3. Study site participation may be discontinued if the investigator judges it necessary for medical, safety, regulatory or other reasons consistent with applicable laws, regulations and good clinical practice.

3.6. Subject Replacement

To account for the dropout rate, 25 participants will be recruited for minimal sample size of 20 subjects. A new subject will only be recruited if number of subjects drop below 20.

4. TRIAL SCHEDULE

4.1. Study Visits and Procedures

(a) Visit 1 - Screening

Volunteers will be interviewed and screened by study personnel. If the volunteer satisfies the inclusion and exclusion criteria, a written informed consent will be obtained from all selected volunteers prior to their participation in the study. Volunteers will have the study explained to them by a study personnel, will read the consent form, have the opportunity to ask questions, and then sign the approved written Informed Consent form and keep a copy. The study personnel will then proceed to schedule visit 2 and 3 with the participant.

(b) Visit 2 - Installation of CGMS (Day 1)

Upon arrival, the participant will be educated on how to maintain and care for a CGMS and to keep a food and activity diary for the duration of the CGM. During this period (Day 1-14), participants will receive SMS to check on the CGMS. If there is a need, the research personnel will arrange for a mutually convenient time and place to review and replace the CGMS. Then, the participants will proceed to take the first MMTT.

Mixed meal tolerance test (MMTT)

Before the test, measurement of participants' height, BMI, waist and hip circumference, will be done and recorded. Next, participants will be asked to attend the MMTT protocol. The participant will need to fast (no food or drinks, except plain water) from 10 pm the night before or for approximately 10-12hr prior to the study visit. No food except clear water should be

consumed. A cannula will be inserted into the participant's forearm and the cannula will remain for blood sampling only. A fasting sample will be taken for the immediate measurement of glucose while other samples for insulin, gut hormones (GLP-1, GIP, Peptide YY, Ghrelin, and Glucagon), and other metabolites will be taken, processed, stored and analysed in batches at a later stage. Then, the participant will be given either mixed meal with controlled rice or mixed meal with test rice. At 0, 15, 30, 45, 60, 90, 120 minutes, blood will be sampled through a cannula from one of the arms. Subjects will be asked to remain seated throughout the visit and only minimal movement is allowed. Blood-taking will be conducted in room designated and approved for phlebotomy purposes. Only trained personnel and/or trained nurses will be conducting the blood drawn.

At each time point, the participant will also be given a visual analogue scale (VAS) to indicate how they feel in response to given statements by marking an "X" on a 100-mm line. For example, "How strong is your desire to eat? " Response: Very weak (0 mm) to very strong (100 mm). Appetite was evaluated using a 100 mm VAS. At time 15 min, palatability of the treatment will be assessed by five characteristics, from bad (0 mm) to good (100 mm). These characteristics were visual appeal, smell, taste, texture, and overall pleasantness of the meal given. Scores were determined by measuring the distance (in mm) from the left starting point of the line to the intersection of the "X". The average scores and AUC will be calculated and compared between the two meals

(c) Continuous glucose monitoring (Day 1 - 14)

For the next 14 days, participants will be provided with lunch and dinner from the research team through delivery. They will be randomized to receive either mixed meal with controlled rice or mixed meal with Fibre Grain rice for day 1 to 7 and received the alternative for the day 8- 14. Participants will not be told whether they are receiving the Fibre Grain rice or control rice

(d) Visit 3 (Day 14 of CGM) – MMTT2 and removal of CGMS

On day 14, participants will return to undergo the second MMTT. Their height, BMI, waist and hip circumference will be measured and recorded. Participants will be asked to attend the same MMTT protocol (refer to Day 1 – MMTT protocol). Lastly, they will return the CGMS, and your 14-day food and activity diary

